5.3. Lifestyle Considerations

5.3.1. Contraception

The investigator or his or her designee, in consultation with the participant, will confirm that the participant has selected an appropriate method of contraception for the individual participant and his or her partner(s) from the permitted list of contraception methods (see [Appendix 4, Section 10.4.4](#)) and will confirm that the participant has been instructed in its consistent and correct use. At time points indicated in the schedule of activities ([SOA](#)), the investigator or designee will inform the participant of the need to use highly effective contraception consistently and correctly and document the conversation and the participant's affirmation in the participant's chart (participants need to affirm their consistent and correct use of at least 1 of the selected methods of contraception) considering that their risk for pregnancy may have changed since the last visit. In addition, the investigator or designee will instruct the participant to call immediately if the selected contraception method is discontinued or if pregnancy is known or suspected in the participant or partner.

5.4. Screen Failures

Screen failures are defined as participants who consent to participate in the clinical study but are not subsequently enrolled in the study. A minimal set of screen failure information is required to ensure transparent reporting of screen failure participants to meet the CONSORT publishing requirements and to respond to queries from regulatory authorities. Minimal information includes demography, screen failure details, eligibility criteria, and any SAE.

Individuals who do not meet the criteria for participation in this study (screen failure) may be rescreened, up to a limit of 1 time.

6. STUDY INTERVENTION(S) AND CONCOMITANT THERAPY

Study intervention is defined as any investigational intervention(s), marketed product(s), placebo, medical device(s), or study procedure(s) intended to be administered to a study participant according to the study protocol.

For the purposes of this protocol, study intervention refers to investigational product.

6.1. Study Intervention(s) Administered

Intervention Name	PF-07260437	
Arm Name (group of participants receiving a specific treatment (or no treatment)	All	
Type	Biologic	
Dose Formulation	Powder for solution for injection	Solution for injection
Unit Dose Strength(s)	15 mg/vial	15 mg/mL, 1 mL per vial
Dosage Level(s)	Dose amount and frequency – reference the study scheme/figure or text below as appropriate	
Route of Administration	SC or IV	
Use	Experimental	
IMP or NIMP	IMP	
Sourcing	Provided centrally by the sponsor. Reference IP manual for supply distribution process details.	
Packaging and Labeling	Study intervention will be provided in vials. Each vial will be labeled as required per country requirement. Study intervention will be provided as open-label product.	
Current/Former Name(s) or Alias(es)	PF-07260437, B7-H4 bispecific antibody	

Each single-use vial of liquid formulation contains 1 mL of PF-07260437 15 mg/mL. The vial is sealed with a coated stopper and an overseal and is labeled according to local regulatory requirements.

Inpatient Observation

For PF-07260437 administration without a priming dose, all participants will be observed inpatient for at least 48 hours after the first SC dose (or the first IV dose, as applicable) on C1D1 and for at least 8 hours after the second SC dose (or the second IV dose, as applicable) on C1D15 and for at least 1 hour post dose for all subsequent outpatient visits to closely manage and monitor acute toxicities.

For PF-07260437 administration with a priming dose, all participants will be observed inpatient for at least 24 hours after the first SC injection (or the first IV dose administration, as applicable) on C1D1 and for at least 24 hours after the second (full) SC dose (or the second [full] IV dose, as applicable) on C1D15 to closely manage and monitor acute toxicities. Participants should be observed for at least 1 hour post SC dose for all outpatient visits starting with C2D1 in both cohorts until the investigator has confirmed the participant has not exhibited signs of CRS (Table 7). Additional inpatient observation for subsequent cycles of IV dosing beyond Cycle 1 may be considered based on the investigator's discretion and should be discussed with the sponsor.

In addition, participants who experience \geq Grade 3 infusion-related adverse events (IV administration) or clinically significant CRS must be hospitalized for at least 24 hours for at least 4 subsequent doses (two cycles).

Modification of inpatient observation period might be allowed based on emerging safety data and will require discussion and agreement between investigator and sponsor.

6.1.1. Administration

6.1.1.1. Premedication

Prophylactic premedication for infusion related reaction, allergic reaction or CRS is not allowed during the DLT evaluation period during initial dose escalation. However, if the participant experiences an infusion related reaction (IV), significant injection site reaction, CRS, fever/chills, nausea/vomiting, hypotension, or pain, appropriate treatment should initiate and premedication as prophylaxis may be considered for subsequent cycles as follows:

- Acetaminophen 650 mg (or equivalent), oral
- Diphenhydramine 25 mg, oral or IV
- Dexamethasone 10 mg (or equivalent), oral or IV

Modifications to the premedication regimen (eg, frequency of premedication, doses of individual agents, removal, or addition of agents) may be allowed per hospital or local clinical practice after discussion and agreement between the sponsor and investigator.

Based on a review of all accumulated safety data (eg, $\geq 50\%$ of participants experienced significant allergic reaction or CRS related symptoms and signs), prophylactic premedication may be considered for new participants after agreement between investigators and the sponsor to determine the MTD/RDE with prophylaxis.

In addition, depending on accumulated safety data, prophylactic premedication during cycle 1 after identification of the maximum tolerated dose (MTD)/recommended dose for expansion (RDE) may be allowed.

The pre-treatment medication will not be supplied by sponsor.

6.1.1.2. SC Administration

Qualified and trained investigational site personnel will administer PF-07260437 to participants by SC injection. PF-07260437 will be administered at a flat dose via SC injection Q2W at 28-day cycles (on Day 1 and Day 15) until the participant meets one of the study intervention discontinuation criteria (See [Section 7.1](#)). Participants should have SC injections in the abdomen with preference to the lower quadrants when possible. For participants receiving 2 or more SC injections, PF-07260437 should be administered in 2 or more different quadrants of the abdomen (with preference given to the lower quadrant when possible); 1 or 2 injections per quadrant. The injection can be rotated with each administration for participant comfort. Refer to [Appendix 14](#), for details on administration of multiple injections to the abdomen.

Each injection volume may be up to 2 ml in volume. If an institutional policy sets a maximum volume <2 ml, the number of injections may be increased to ensure that the correct volume is administered. Refer to the IP Manual for specific instructions on the handling and preparation of study treatment.

Refer to [Table 7](#) for required inpatient observation stays following PF-07260437 administration.

6.1.1.3. IV Administration

If IV route is evaluated. Qualified and trained investigational site personnel will administer PF-07260437 to participants by IV infusion. PF-07260437 will be administered at a flat dose intravenously over approximately 60 minutes (± 15 minutes) Q2W at 28-day cycles (on Day 1 and Day 15) until the participant meets one of the study intervention discontinuation criteria (see [Section 7.1](#)).

If IV route is evaluated, a 1-hour infusion and inpatient monitoring in a hospital for at least 48 hours after the first dose in Cycle 1 in dose escalation will be implemented. Additional inpatient observation for subsequent cycles beyond Cycle 1 may be considered based on the investigator's discretion and should be discussed with the sponsor as described in [Section 6.1](#).

Details for preparation of PF-07260437 infusion are provided in the IP Manual.

6.2. Preparation, Handling, Storage and Accountability

1. The investigator or designee must confirm appropriate temperature conditions have been maintained during transit for all study interventions received and any discrepancies are reported and resolved before use of the study intervention.
2. Only participants enrolled in the study may receive study intervention and only authorized site staff may supply or administer study intervention. All study interventions must be stored in a secure, environmentally controlled, and monitored (manual or automated recording) area in accordance with the labeled storage conditions with access limited to the investigator and authorized site staff. At a minimum, daily minimum and maximum temperatures for all site storage locations must be documented and available upon request. Data for nonworking days must indicate the minimum and maximum temperatures since previously documented for all site storage locations upon return to business.
3. Any excursions from the study intervention label storage conditions should be reported to Pfizer upon discovery along with any actions taken. The site should actively pursue options for returning the study intervention to the storage conditions described in the labeling, as soon as possible. Once an excursion is identified, the study intervention must be quarantined and not used until Pfizer provides permission to use the study intervention. Specific details regarding the definition of an excursion

and information the site should report for each excursion will be provided to the site in the IP manual.

4. Any storage conditions stated in the SRSD will be superseded by the storage conditions stated on the label.
5. Study interventions should be stored in their original containers.
6. See the IP manual for storage conditions of the study intervention once reconstituted and/or diluted. Specific details of the dilution are provided in the IP Manual.
7. The investigator, institution, or the head of the medical institution (where applicable) is responsible for study intervention accountability, reconciliation, and record maintenance (ie, receipt, reconciliation, and final disposition records), such as the IPAL or sponsor-approved equivalent. All study interventions will be accounted for using a study intervention accountability form/record.
8. Further guidance and information for the final disposition of unused study interventions are provided in the IP manual. All destruction must be adequately documented. If destruction is authorized to take place at the investigator site, the investigator must ensure that the materials are destroyed in compliance with applicable environmental regulations, institutional policy, and any special instructions provided by Pfizer.

Upon identification of a product complaint, notify the sponsor within 1 business day of discovery as described in the IP manual.

6.2.1. Preparation and Dispensing

A qualified staff member will dispense the study intervention using the IRT system via unique container numbers in the vials provided, in quantities appropriate according to the participant's dose. A second staff member will verify the dispensing.

See the IP manual for instructions on how to prepare the study intervention for administration. Study intervention should be prepared and dispensed by an appropriately qualified and experienced member of the study staff (eg, physician, nurse, physician's assistant, nurse practitioner, pharmacy assistant/technician, or pharmacist) as allowed by local, state, and institutional guidance. Vials are single use.

Only qualified personnel who are familiar with procedures that minimize undue exposure to themselves and to the environment should undertake the preparation, handling, and safe disposal of PF-07260437.

6.3. Measures to Minimize Bias: Randomization and Blinding

6.3.1. Allocation to Study Intervention

For Part 1:

Study intervention will be dispensed at the study visits summarized in the [SOA](#).

Returned study intervention must not be redispensed to the participants.

The study-specific IRT reference manual and IP manual will provide the contact information and further details on the use of the IRT system

Dose level allocation in Part 1 will be performed by the sponsor after participants have given their written informed consent and have completed the necessary screening assessments. The site staff will fax/email a complete Participant Registration Form to the designated sponsor study team member or designee. The sponsor will assign a participant identification number and supply this number to the site. The participant identification number will be used on all study related documentation at the site.

No participant shall receive investigational product/study intervention until the investigator or designee has received the following information in writing from the sponsor:

- Confirmation of the participant's enrollment;
- Specification of the dose level for that participant and;
- Permission to proceed with dosing the participant.

In Part 1, sites will use the IRT for drug supply and inventory management.

For Part 2:

Allocation of participants in Part 2 of the study to treatment groups may proceed through the use of an IRT system (TWR). The site personnel (study coordinator or specified designee) will be required to enter or select information including but not limited to the user's ID and password, the protocol number, and the participant number. The site personnel will then be provided with a treatment assignment, randomization number, and DU or container number when study intervention is being supplied via the IRT system. The IRT system will provide a confirmation report containing the participant number, randomization number, and DU or container number assigned. The confirmation report must be stored in the site's files.

Study intervention will be dispensed at the study visits summarized in the [SOA](#).

Returned study intervention must not be redispensed to the participants.

The study specific IRT reference manual and IP manual will provide the contact information and further details on the use of the IRT system.

6.4. Study Intervention Compliance

When participants are dosed at the site, they will receive study intervention directly from the investigator or designee, under medical supervision. The date and time of each dose administered in the clinic will be recorded in the source documents and recorded in the CRF. The dose of study intervention and study participant identification will be confirmed at the

time of dosing by a member of the study site staff other than the person administering the study intervention.

The site will complete the required dosage Preparation Record located in the IP manual. The use of the Preparation Record is preferred, but it does not preclude the use of an existing appropriate clinical site documentation system. The existing clinical site's documentation system should capture all pertinent/required information on the preparation and administration of the dose. This may be used in place of the Preparation Record after approval from the sponsor and/or designee.

6.5. Dose Modification

Every effort should be made to administer study intervention on the planned dose and schedule. In the event of significant toxicity, which may include a DLT, dosing may be delayed, reduced, or discontinued as described below. In the event of multiple toxicities, dose modification should be based on the worst toxicity observed. Participants are to be instructed to notify investigators at the first occurrence of any adverse symptom. In addition to dose modifications, investigators are encouraged to employ best supportive care according to local institutional clinical practices.

Toxicities potentially related to PF-07260437 should be managed according to the dose modifications described in [Table 10](#) and [Table 11](#).

Selected toxicities that do not resolve or worsen following supportive care and dose modifications and with a clinical presentation consistent with a potential irAE without a clear alternative explanation, may require treatment with corticosteroids or other immunosuppressants and should be managed according to the management of irAEs as described in [Section 10.3.5](#).

CRS should be managed according to the CRS Mitigation and Management guidance as described in [Appendix 11](#).

6.5.1. Dosing Interruptions

With respect to study intervention, participants experiencing Grade 3 or 4 potentially treatment-related toxicity or intolerable Grade 2 toxicity despite supportive treatment should have their treatment interrupted as indicated in [Table 10](#) and [Table 11](#).

Appropriate follow-up assessments should be done until adequate recovery occurs as assessed by the investigator. Criteria required before treatment can resume are described in [Section 6.5.2](#).

Doses may be held up to 4 weeks until toxicity resolution. Depending on when the AE resolved, a treatment interruption may lead to the participant missing subsequent planned doses within that same cycle or to delay the initiation of the subsequent cycle as follows:

- If the planned Day 1 dose (of any cycle) cannot be administered due to an AE, then Day 1 dose will be delayed until the AE has resolved and the study drug can be administered.
- If the planned Day 15 dose (of any cycle) is delayed for ≤ 7 days, then the planned day 15 dose can be administered as the delayed Day 15 dose. Day 1 of the subsequent cycle will be administered 2 weeks after the delayed Day 15 dose.
- If the planned Day 15 dose (of any cycle) is delayed for >7 days, then Day 15 will be skipped. The next dose will be administered when the AE has resolved and will be considered the Day 1 dose of the subsequent cycle.

The need for a dose reduction at the time of treatment resumption should be based on the criteria defined in the [Dose Reductions section](#), unless expressly agreed otherwise following discussion between the investigator and the sponsor.

In the event of a treatment interruption for reasons other than treatment-related toxicity (eg, elective surgery) lasting >4 weeks, treatment resumption will be decided in consultation with the sponsor.

See [Appendix 8, Section 10.8.4](#) for COVID-19 related dose interruption.

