Visit Identifier Abbreviations used in this table may be found in Appendix 17	Screening	Treatment Period									EOT	4-week Follow- up	90-day Follow- up for irAEs	Notes
		Cycle 1 =28 days				Cycle ≥ 2 (28 days)								
Study Day	-28 to -1	1	2 ^a	8	15	16 ^a	22	1	8 ^b	15				
 Additional visit window may be allowed after discussion and agreement between investigator and sponsor. 
a: End of inpatient observation (PK, ECG, vital signs).
 
b: This D8 visit is only applicable for Cycles 2 and 3, whereas, C3D8 is applicable for PK/PD and ECG only.

Visit Window (days)		± 2		± 2	± 2			± 2	± 2	± 2		± 7	± 7	
Study Intervention														
PF-07260437		X (priming dose)		(X ^c)	X			X		X				
 C1D1 is priming dose and C1D15 is full/maintenance dose. c: A 2-step priming may be considered on C1D1 and C1D8. See Section 4.1 for additional information.

Table 3. Study Schedule of Assessments – Part 1 With Priming

Visit Identifier Abbreviations used in this table may be found in Appendix 17	Screening	Treatment Period									EOT	4-week Follow- up	90-day Follow- up for irAEs	Notes
		Cycle 1 =28 days												
Study Day	-28 to -1	1	2 ^a	8	15	16 ^a	22	1	8 ^b	15				
 Additional visit window may be allowed after discussion and agreement between investigator and sponsor.
Visit Window (days)		±2	±2	±2		±2	±2	±2	±2	±2		±7	±7	
a: End of inpatient observation (PK, ECG, vital signs).
 
b: This D8 visit is only applicable for Cycles 2 and 3, whereas, C3D8 is applicable for PK/PD and ECG only.

Premedication		(X)	(X ^d)	(X)			(X)		(X)					
 Prophylactic premedication is not allowed during the DLT evaluation period during initial dose escalation. However, if the participant experiences an infusion related reaction (IV), allergic reaction, significant injection site reaction, CRS, fever/chills, allergic reaction, nausea/vomiting, hypotension, or pain, appropriate treatment should initiate and premedication as prophylaxis may be considered for subsequent injections as well as for new participants. See Section 6.1.1.1 for additional information. d: Only applicable to 2-step priming

Table 3. Study Schedule of Assessments – Part 1 With Priming

Visit Identifier Abbreviations used in this table may be found in Appendix 17	Screening	Treatment Period									EOT	4-week Follow- up	90-day Follow- up for irAEs	Notes

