6.5.3. Dose Reductions

Following dosing interruption or cycle delay due to toxicity, the PF-07260437 dose may need to be reduced when treatment is resumed.

No specific dose adjustments are recommended for Grade 1 or 2 treatment-related toxicity. However, investigators should always manage their participants according to their medical judgment based on the particular clinical circumstances.

Dose reduction of PF-07260437 by 1 and, if needed, 2 dose levels (See Table 9) will be allowed depending on the type and severity of toxicity encountered. Participants requiring more than 2 dose reductions will be discontinued from the treatment and entered into the Follow-up phase, unless otherwise agreed between the investigator and the sponsor. All dose modifications/adjustments must be clearly documented in the participant's source notes and CRF.

Once a dose has been reduced for a given participant, all subsequent cycles should be administered at that dose level, unless further dose reduction is required. Intraparticipant dose re-escalation is not allowed.

Table 9. Available Dose Reduction Levels From Starting Dose

Dose Level	PF-07260437 SC	PF-07260437 IV
Starting dose	100 µg Q2W	60 µg Q2W
-1	60 ug Q2W (one dose level below starting dose)	N/A

Participants experiencing a DLT may resume dosing at the next lower dose level (if applicable) once adequate recovery is achieved, and in the opinion of the investigator and sponsor, the participant is benefiting from therapy.

In some cases, participants experiencing recurrent and intolerable Grade 2 toxicity may reduce the dose to the next lower dose level once recovery to Grade ≤ 1 or baseline is achieved.

Recommended dose modifications of PF-07260437 for non-immune related toxicity are described in Table 10.

Table 10. Dose Modifications for Study for Non-Immune-Related Toxicity

Toxicity	Grade 1	Grade 2	Grade 3	Grade 4
Nonhematologic (except pancreatitis)	Continue at the same dose level.	Continue at the same dose level.	Withhold dose until toxicity is Grade <1 , or has returned to baseline, then resume treatment at the same dose level or reduce the dose by 1 level at the discretion of the investigator.*	Withhold dose until toxicity is Grade <1 , or has returned to baseline, then reduce the dose by 1 level or 2 levels, or permanently discontinue at the discretion of the investigator.*

Table 10. Dose Modifications for Study for Non-Immune-Related Toxicity

Toxicity	Grade 1	Grade 2	Grade 3	Grade 4

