9.1. Statistical Hypotheses

There will be no formal hypothesis testing in this study.

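### In primed cohorts the Section 6.5.1 skip rule can move the first full dose to C2D1, and the sampling and observation keyed to C1D15 do not clearly move with it

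*Protocol*

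**What the plan says.** Protocol Section 6.5.1 covers delayed doses in every cycle: "If the planned Day 15 dose (of any cycle) is delayed for >7 days, then Day 15 will be skipped". It continues: "The next dose will be administered when the AE has resolved and will be considered the Day 1 dose of the subsequent cycle". It also says: "Doses may be held up to 4 weeks until toxicity resolution". A Day 15 dose that is late by 7 days or less is still given as Day 15. Nothing in Section 6.5 mentions priming.

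In primed cohorts the two Cycle 1 doses differ. Table 3 says: "C1D1 is priming dose and C1D15 is full/maintenance dose".

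Section 6.1 requires inpatient observation in primed cohorts "for at least 24 hours after the second (full) SC dose", and places that dose on C1D15. The same paragraph then says: "Participants should be observed for at least 1 hour post SC dose for all outpatient visits starting with C2D1 in both cohorts". Table 7 has a C1D15 column (24 hours with priming). All other outpatient visits get 1 hour in Part 1 and are left to the investigator in Part 2. For Part 2 with priming, Tables 5 and 7 give 24 hours on C1D15, and Section 4.1 says up to 24 hours after the first full dose.

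On dose levels, Section 6.5.3 says: "Participants experiencing a DLT may resume dosing at the next lower dose level (if applicable) once adequate recovery is achieved". Neither that section nor Tables 9 and 10 say whether the level in a primed cohort is that of the priming dose or the full dose.

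**The concern.** Section 6.5.1 is written as if the Day 1 and Day 15 doses were interchangeable, although this is an inference from its silence on priming. In a primed cohort they are not. C1D15 is the first exposure to the full dose, and Section 4.3.2 gives reducing the rate and grade of CRS as the reason for priming. The participants concerned have had an adverse event on the priming dose that held treatment for more than a week. If the day label governs, their first full dose has none of the planned post-dose pharmacology samples, and the site has two observation durations to choose from. What is at stake is safety monitoring and PK and cytokine information on that first exposure, in a first-in-human study.

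**Working it through.** No hypothesis test or sample-size formula is involved ("There will be no formal hypothesis testing in this study"). The check is a day count and a reading of the schedule tables.

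**The plan's own figure.** Section 4.3.6 gives a 42-day DLT window with one priming dose. Priming interval 14 days + two full-dose intervals 2 × 14 = 28 days gives 14 + 28 = 42. Day 43 − 28 = Day 15 of Cycle 2, as stated. The figure reproduces.

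**Delay traced from Day 15 under Section 6.5.1.**

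| Delay (days) | First full dose on | Label |
|---|---|---|
| 0 | Day 15 | C1D15 |
| 7 | 15 + 7 = Day 22 | C1D15 |
| 8 | 15 + 8 = Day 23 | C2D1 |
| 28 (the 4-week limit) | 15 + 28 = Day 43 | C2D1 |

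The label changes between a 7-day and an 8-day delay, although the dose is the same.

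**Scheduled samples after the first full dose, SC, Part 1 (Table 4; code A is Cycle 1, code B is Cycle 2).**
- PK: 4, 8, 24 and 168 h carry code A. None carries B. 4 falls to 0.
- Central cytokines: 1, 4, 8, 24 and 168 h carry A. None carries B. 5 falls to 0.
- Soluble B7-H4: 4, 8, 24 and 168 h carry A. None carries B. 4 falls to 0.
- Immunophenotyping: the post-dose samples also carry only A.

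For blood samples, code B appears only at Day 1 pre-dose. The Day 16 check (ECG and vital signs at the end of the inpatient stay) and the routine injection-site assessment are likewise Cycle 1 items. Section 8.2.6 continues injection-site assessment after Cycle 1 only if symptoms persist. Part 2 (Table 6) shows the same pattern: Cycle 2 blood samples are pre-dose only.

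**Observation of the moved dose.** It is the second dose and a full dose, which points to at least 24 hours. It is also C2D1, which points to at least 1 hour (Part 1) or investigator's discretion (Part 2). Sections 4.1 and 6.1 require at least 24 hours in hospital for at least 4 later doses after clinically significant CRS or a Grade 3 or higher infusion-related event. Other toxicities that withhold dosing, such as Grade 2 pancreatitis (Table 10) or Grade 2 hepatitis (Table 11), do not trigger that rule.

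**Effect on the dose-escalation model.** Treatment-related Grade 3 or higher non-hematologic toxicity is generally already a DLT (Section 4.3.6.2, with listed exceptions). A participant without a DLT who skips C1D15 has not received all planned doses (Section 4.3.6), nor 100% of dosing in Cycles 1 and 2 (SAP Table 1), and is not DLT-evaluable. What remains is a first DLT after the moved dose but inside the window. On the SAP's 42 days, a dose on Day 23 leaves 42 − 23 + 1 = 20 days; a dose on Day 43 leaves none.

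**Reference dose (secondary).** Take the Table 8 levels with CRS at 900 µg. Section 4.1 then gives a 300 µg priming dose and a full dose of at most 900 µg. After a DLT on 300 µg, one level below a 900 µg full dose is 300 µg, and one level below the priming dose is 100 µg. The text does not choose. On the second reading, Section 6.5.3's bar on re-escalation would also rule out the planned step-up.

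**The case against.** The strongest reply is that little is lost in practice.

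- *Safety data remain.* Table 3 schedules a C2D8 visit in primed Part 1 cohorts with examination, vital signs, ECG, hematology and chemistry, and C2D1 keeps its pre-dose ECG. Suspected CRS triggers extra PK, cytokine and soluble B7-H4 samples. This stands, so a reader who infers that no post-dose data are collected goes too far. Table 5 shows no such Day 8 visit in Part 2.
- *Observation can be read as preserved.* Section 6.1 ties 24 hours to the second (full) dose as well as to C1D15. One hour is a minimum, so a 24-hour stay meets both rules. Table 3 allows conditional inpatient observation from Cycle 2, and the Table 7 footnote bars release until clinically significant CRS is ruled out. This also stands. The documents do not establish that observation drops to 1 hour; they leave open which duration governs.
- *Sampling can be rearranged.* Section 8.4 allows missed PK samples to be rescheduled and time points added without an amendment. That permits a case-by-case repair but does not require one.
- *A reduction ordinarily means below the dose that caused the event.* That is the natural reading. A reader might infer that the protocol directs resumption at or above the dose that caused a DLT. It does not; the reference dose is undefined.

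**Conclusion.** The point holds in a limited form. Followed literally, the relabelling rule detaches the first full dose from its scheduled post-dose PK, cytokine, soluble B7-H4 and immunophenotyping samples, the Day 16 check and the routine injection-site assessment. It also leaves two observation requirements on one dose. In Part 1 with SC dosing the loss is 4 PK and 5 cytokine times per affected participant. The sampling gap does not depend on how Section 6.1 is read; the observation gap does, and it is absent where the mandatory 24-hour stay already applies.

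A reader might infer that the dose-escalation model or the RDE is materially distorted. The documents do not support that, because most affected participants already have a DLT or are not DLT-evaluable.

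The conclusion assumes that priming is used, which the protocol makes conditional, and that a toxicity delays C1D15 by more than 7 days. The documents give no rate for such delays. Sample counts are read from tables extracted from PDF. This should be fixed before any primed cohort opens. The reference dose in Section 6.5.3 is a secondary clarification.

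**What to change.** Reconcile Section 6.5.1 with Section 6.1, Table 7 and Tables 3 to 6. Key every requirement now labelled C1D15 to the dose itself: the first full dose with priming, the second dose without. When C1D15 is skipped, the post-dose samples, the next-day check, the injection-site assessment and whichever observation requirement the sponsor intends then move with the dose. Naming the first full dose also covers two-step priming, where it is the third dose given.

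State in Section 6.5.3 and Tables 9 and 10 which dose, priming or full, is the reference for the same or the next lower level in a primed cohort. The clinical rule and the observation period are for the sponsor to decide; none is proposed here.

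The cost is protocol wording and schedule footnotes. Samples are moved, not added.
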